6.1.2 Data Collection/Recording Exceptions

6.1.2.1 Abnormal Laboratory Values

An abnormal laboratory value will be recorded as an AE **only** if the laboratory abnormality is characterized by any of the following:

- Results in discontinuation from the study
- Is associated with clinical signs or symptoms
- Requires treatment or any other therapeutic intervention
- Is associated with death or another serious adverse event, including hospitalization
- Is judged by the Investigator to be of significant clinical impact
- If any abnormal laboratory result is considered clinically significant, the investigator will provide details about the action taken with respect to the test drug and about the patient's outcome.

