3.2 DOSE LIMITING TOXICITY

A dose-limiting toxicity (DLT) is defined as: any treatment-emergent and related severe (grade \geq 3) toxicity, i.e., toxicity deemed related to lenalidomide, romidepsin and/or CC-486 (5-azacitidine) by the PI or designee and occurring during the MTD observation time, defined as day -7 until end of cycle 1 (normally day 22). Each patient must receive all doses of the investigational medications during cycle 1 to be considered as successfully completing the DLT evaluation period.

The following toxicities and conditions will be recorded, however they will not be considered to be DLTs:

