3.2.1 Hematologic exceptions

- Grade 3 or 4 lymphocytopenia without clinical signs of infection grade 2 or above.
 - Lenalidomide, romidepsin and CC-486 (5-azacitidine) will be continued in the event of asymptomatic grade 3 or 4 lymphocytopenia, unless there are clinical signs of significant infection (persistent fevers, labile blood pressure, localized complaints or findings on physical examination, hypoxia or organ dysfunction).
- Grade 3 neutropenia without clinical signs of infection grade 2 or above.
 - Lenalidomide, romidepsin and CC-486 (5-azacitidine) will be continued in the event of grade 3 neutropenia unless there are clinical signs of significant infection, as listed above.
- Grade 3 thrombocytopenia without signs of bleeding that resolved within 7 days of holding the study drug(s) (See Section 3.5.1 for study drug holding parameters).
- Grade 3 anemia that improves to Grade ≤ 2 after transfusion of up to two units of pRBCs and does not recur within 7 days.
- Grade 3 febrile neutropenia (grade 3 febrile neutropenia at any time during therapy will be considered an SAE but not DLT)

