3.2.2 Non-Hematologic exceptions

- Transient (< 72 hours) grade 3 hypoalbuminemia, hypokalemia, hypomagnesemia, hyponatremia or hypophosphatemia which responds to medical intervention. Lenalidomide, romidepsin and CC-486 (5-azacitidine) will be continued while the metabolic abnormalities are corrected by intravenous or oral supplementation
- Patients who require short term hospitalization (3 days or less) only for fluid and electrolyte disturbances secondary to anorexia, nausea/vomiting/diarrhea which are common AEs for 5-azacitidine, lenalidomide and romidepsin individually and more so for the combination. This exception does not apply to secondary organ dysfunction resulting from this biochemical derangements or patients that require vasopressor BP support.

- Grade 3 rash that resolves to grade ≤ 2 within 7 days of holding the study drug(s) (See Section 3.5.1 for study drug holding parameters).

Management and dose modifications associated with the above adverse events are outlined in Section 3.5. Occurrence of any DLT-defining toxicity after the first 28 days of treatment will lead to dose modification as specified below; however, it will not be deemed a DLT for purposes of dose escalation.

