10.4.2 Analysis of the Primary Endpoints

Safety summaries will include summaries in the form of tables and listings. Reports will include the frequency (number and percentage) of treatment emergent AEs grouped by severity of the AE (per CTCAE, v5.0) and by relationship to study drug (e.g., lenalidomide, romidepsin, CC-486 (5-azacitidine) in any combinations).

Laboratory shift tables containing counts and percentages will be prepared by treatment assignment, laboratory parameter, and time. Summary tables will be prepared for each laboratory parameter. Figures of changes in laboratory parameters over time will be generated.

Results of vital sign assessments, ECGs, and physical exams will be tabulated and summarized.

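### The primary AE-by-grade table may under-count asymptomatic, untreated grade 3-4 laboratory toxicity, because Section 6.1.2.1 admits laboratory AEs by consequence or judgement and not by grade

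*Combined protocol and SAP*

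**What the plan says.** Section 6.1.2.1 sets a filter. It limits the cases in which "An abnormal laboratory value will be recorded as an AE" to a list of five triggers: discontinuation from the study, clinical signs or symptoms, "Requires treatment or any other therapeutic intervention", association with death or another SAE, and "Is judged by the Investigator to be of significant clinical impact". A further bullet asks for details of any clinically significant result. CTCAE grade is not on the list, and neither is a hold, delay or reduction of a study drug.

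Three other places bear on the same values:

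- Section 3.2 introduces the DLT exceptions with "The following toxicities and conditions will be recorded, however they will not be considered to be DLTs". The first exception in 3.2.1 is "Grade 3 or 4 lymphocytopenia without clinical signs of infection grade 2 or above". The three investigational drugs "will be continued in the event of asymptomatic grade 3 or 4 lymphocytopenia", unless there are signs of significant infection.
- Section 8.1.1 defines an AE so as to include an abnormal laboratory finding, without the 6.1.2.1 filter.
- Section 10.1 makes the frequency of treatment-emergent AEs a primary endpoint. Section 10.4.2 reports the "frequency (number and percentage) of treatment emergent AEs grouped by severity of the AE" and by relationship to study drug. It also plans laboratory shift tables, summaries per parameter and figures, without naming CTCAE grade as the shift category.

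**The concern.** A table of AEs by grade can show only what was recorded as an AE. If a grade 3 or 4 laboratory value reaches the AE record only through its consequences or through one investigator's judgement, the severe-toxicity rate in a primary output depends partly on that judgement. All three investigational drugs affect blood counts, so the laboratory categories are where this matters most. The protocol does not say whether the exempt events that Section 3.2 wants recorded are to be AE entries, laboratory data or something else, so two study staff could follow the text and produce different AE tables.

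**Working it through.** No figure in the plan underlies this point, so there is nothing to reproduce. The check sets each type of severe laboratory event against the five triggers and then gauges the possible size.

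**Step 1: which events pass the filter on the protocol's own wording?**

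| Event | Handling in the protocol | Objective trigger met? |
|---|---|---|
| Exempt grade 3 anemia | Transfused (3.2.1) | Yes, treatment |
| Exempt grade 3 electrolyte or albumin changes | "abnormalities are corrected by intravenous or oral supplementation" (3.2.2) | Yes, treatment |
| Grade 3 febrile neutropenia | Declared an SAE (3.2.1) | Yes |
| Grade 3 neutropenia given G-CSF | Table 6 lists growth factor in cycle 1 and in cycles 2-6 | Yes, treatment |
| Grade 3-4 thrombocytopenia without bleeding, cycles 2-6 | Table 6 lists holds and dose reductions, no transfusion | Unclear: a hold is not defined as an intervention |
| Asymptomatic grade 3-4 lymphocytopenia | Drugs continued, no treatment described (3.2.1) | No |

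The last two rows reach the AE table only through investigator judgement, unless a hold is read as an intervention. The discontinuation trigger helps little. It refers to leaving the study, and the off-study criteria in 3.11.2 do not include toxicity. Stopping therapy for toxicity falls under 3.11.1, which is a different event.

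**Step 2: how common are these events in the background data?**

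- Romidepsin/5-azacitidine (Table 5, n = 25): grade 3-4 lymphocyte decrease 8/25 = 32%; platelet decrease 12/25 = 48%.
- Romidepsin/lenalidomide (Table 5.1): lymphocyte decrease, grade 3 in 16 and grade 4 in 9. The denominator is not printed; 16/49 = 33% and 9/49 = 18% match the printed percentages, so n = 49 is inferred. If the two grades are different patients, (16 + 9)/49 = 25/49 = 51%. For platelets, (18 + 8)/49 = 26/49 = 53%.

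**Step 3: how many patients could be left out?** Take lymphocytopenia, the clearest case. Expected patients left out = n × r × f, where n is the number of patients, r the background rate and f the share of cases meeting no trigger. The documents do not give f, so it is varied. Section 10.2 gives n = 9 at the MTD and a maximum enrolment of 30.

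- All grade 3-4 cases: 9 × 0.32 = 2.9 to 9 × 0.51 = 4.6 at the MTD; 30 × 0.32 = 9.6 to 30 × (25/49) = 15.3 overall.

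| f | Left out of 9 | Left out of 30 |
|---|---|---|
| 0 | 0 | 0 |
| 0.25 | 0.7 to 1.1 | 2.4 to 3.8 |
| 0.5 | 1.4 to 2.3 | 4.8 to 7.7 |
| 1.0 | 2.9 to 4.6 | 9.6 to 15.3 |

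The range runs from none to all. It shows what is possible and is not an estimate.

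**The case against.** Recording laboratory AEs by consequence is a legitimate design choice, and Section 6.1.1 uses the same standard when it refers to clinically significant abnormal findings. Most severe laboratory toxicity passes the filter, as the first table shows, and investigator judgement can admit the rest. Severe values are not lost from reporting either: 10.4.2 plans laboratory shift and summary tables under the primary analysis, and 10.4.4 promises a report of toxicities by kind, grade and how often they occurred. All of this stands, and it limits the point to asymptomatic, untreated values. It does not remove it. The shift tables are not specified by CTCAE grade and carry no attribution, and 10.4.4 is one sentence that names no data source.

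Three stronger readings are tempting, and the documents do not support them:

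- A reader might infer that 6.1.2.1 contradicts 3.2. Section 3.2 says the events are recorded but not that they are recorded as AEs. A value kept as laboratory data would satisfy both. The sections are unreconciled, no more.
- A reader might infer that most grade 3-4 lymphopenia will disappear from the AE table. That needs f, which is not given.
- A reader might infer that the AE rates cannot be compared with those of the doublets. That depends on how those studies recorded laboratory events, which Tables 5 and 5.1 do not say.

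The obvious remedy, making every value of grade 3 or higher an AE, also has a real drawback. Table 6 is keyed to treatment-related AEs, and its catch-all grade 4 row for cycle 1 specifies discontinuation and a DLT. Section 3.2.1 exempts asymptomatic grade 4 lymphocytopenia and continues the drugs. A bare grade trigger would sharpen that unresolved difference. If added now without retrospective application, it would also make AE ascertainment differ between cohorts, since Section 3.4.1 reports 20 patients enrolled before the redesign.

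**Conclusion.** The point holds in a limited form. The primary AE-by-grade table may under-count asymptomatic, untreated grade 3-4 laboratory toxicity: mainly lymphocytopenia, and possibly thrombocytopenia managed only by holding or reducing drug. Whether it does so is left to investigator judgement, and 6.1.2.1 is not reconciled with 3.2 or 8.1.1. The size cannot be determined from the documents. For lymphopenia the illustration spans 0 to 4.6 of 9 patients at the MTD and 0 to 15.3 of 30 overall. It assumes that two-drug background rates carry over to this regimen, that n = 49 in Table 5.1, that its grade 3 and grade 4 counts are different patients, and that f lies anywhere between 0 and 1.

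**What to change.** 1. In Section 10.4.2, derive treatment-emergent laboratory toxicity by worst CTCAE v5.0 grade from all laboratory values already collected, for all treated patients in every arm, and report it alongside the primary AE table. This applies one rule to all cohorts and does not depend on judgement.
2. In Section 6.1.2.1, add one trigger: the abnormality led to a hold, delay, reduction or discontinuation of any study drug. Apply it retrospectively to patients already enrolled.
3. In Section 3.2, state where the exempt events are recorded: AE form, laboratory data or both.
4. State that these recording and reporting rules do not alter the DLT definition or any treatment rule. Separately, the sponsor must reconcile 3.2.1 with the Table 6 cycle 1 rows for grade 3 neutropenia (3.2.1 continues treatment, Table 6 holds it) and for any grade 4 AE.

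The cost is a few sentences, a programmed table and some extra data entry. The graded laboratory table needs no new tests, since the study calendar in Section 3.9 already schedules blood counts with differential. Attribution is the real work: under Section 8.2 the relationship of each added AE must be assessed by a qualified investigator, so the retrospective step takes investigator time.

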6.2 DATA SHARING PLANS

6.2.1 Human Data Sharing Plan

What data will be shared?

I will share human data generated in this research for future research as follows:

Coded, linked data in an NIH-funded or approved public repository.

Coded, linked data in another public repository

Coded, linked data in BTRIS (automatic for activities in the Clinical Center)

Identified or coded, linked data with approved outside collaborators under appropriate agreements.

How and where will the data be shared?

Data will be shared through:

An NIH-funded or approved public repository. Insert name or names: [ClinicalTrials.gov](#),

dbGaP.

X BTRIS (automatic for activities in the Clinical Center)

X Approved outside collaborators under appropriate individual agreements.

X Publication and/or public presentations.

When will the data be shared?

X Before publication.

X At the time of publication or shortly thereafter.

6.2.2 Genomic Data Sharing Plan

Unlinked genomic data will be deposited in public genomic databases such as dbGaP in compliance with the NIH Genomic Data Sharing Policy.

6.3 RESPONSE CRITERIA

6.3.1 Response Assessments

Tumor response will be assessed by the investigator using the RECIL 2017 criteria [66] for all patients with T-cell lymphoma other than CTCL. Global Response Score [67], and modified severity weighted assessment tool (mSWAT) [68] will be used for patients with CTCL. For leukemic disease, leukemic cells (ATL, Sezary or T-PLL) as percentage of PBMCs will also be assessed and reported separately and response will be assessed using consensus guideline [69]. Patient will be re-evaluated for response as outlined in the Study Calendar, Section 3.9.

6.3.1.1 Response Criteria for PTCL

RECIL 2017 criteria [66] use the Deauville five-point scale for assessment of response via FDG-PET. The five-point scale (5-PS) has been validated for use at interim staging and at the end of treatment and was adopted as the preferred reporting method at the First International Workshop on PET in Lymphoma in Deauville, France (i.e., Deauville criteria), and in several international trials.

The 5-PS PS scores the most intense uptake in a site of initial disease:

1. if present, as follows: no uptake or no residual uptake (when used at interim)
2. slight uptake, but below blood pool (mediastinum)
3. uptake above mediastinal, but below or equal to uptake in the liver
4. uptake slightly to moderately higher than liver
5. markedly increased uptake or any new lesion (on response evaluation)

The sum of longest diameter (SLD) is used for assessment of tumor burden. In patients with disseminated disease, a maximum of three target lesions should be selected and used to estimate tumor response. Target lesions should be selected from those with the largest size that can be reproducibly measured and preferably representing multiple sites and/organs. In most cases, lymph nodes can be considered target lesions if the lymph node longest diameter measures ≥ 15 mm. A lymph node measuring between 10 and 14 mm is considered abnormal but should not be selected as a target lesion. Lymph nodes measuring < 10 mm in diameter are considered normal. In certain anatomical sites (inguinal, axillary, and portocaval), normal lymph nodes may exist in a narrow, elongated form, and such nodes should not be selected as target lesions if alternatives are available. Extranodal lesions are selected as target lesions if they have soft tissue component, based on their

size, and the ease of reproducibility of repeated measurements, with a minimum measurement of the longest diameter of ≥ 15 mm. All other lesions should be identified as nontarget lesions and should be recorded at baseline, without the need to measure them. Nontarget lesions should be followed and reported as present, absent, or clear progression.

Table 86: Response categories based on assessment of target lesions

% Change in sum of diameters of target lesions from nadir					
	CR	PR	MR	SD	PD
% change from baseline	
 Complete disappearance of all target lesions and all nodes with long axis <10 mm $\geq 30\%$ decrease in the sum of longest diameters of target lesions (PR) with normalization of FDG-PET 	
 $\geq 30\%$ decrease in the sum of longest diameters of target lesions but not a CR 	
 $\geq 10\%$ decrease in the sum of longest diameters of target lesions but not a PR ($<30\%$) 	
 $<10\%$ decrease or $\leq 20\%$ increase in the sum of longest diameters of target lesions 	
 $>20\%$ increase in the sum of longest diameters of target lesions For small lymph nodes measuring <15 mm post therapy, a minimum absolute increase of 5 mm and the long diameter should exceed 15 mm Appearance of a new lesion
FDG-PET	Normalization of FDG-PET (Deauville score 1-3)	Positive (Deauville score 4-5)	Any	Any	Any
Bone marrow involvement	Not involved	Any	Any	Any	Any
New lesions	No	No	No	No	Yes or No

CR, complete response; CT, computerized tomography; FDG-PET, [¹⁸F]2-fluoro-2-deoxy-D-glucose; MR, minor response; PD, progression of disease; PR, partial response; SD, stable disease.

6.3.1.2 Response Criteria for CTCL

Global Response (GR) score ([Appendix B](#)) will be used for assessing response in patients with CTCL [\[67\]](#). GR score incorporates separate responses in each component of the TNBM staging (i.e., skin, nodes, viscera and blood; [Appendix B](#)). No patient with a global OR should have less than a PR in the skin.

The mSWAT [\[68\]](#) is an instrument utilized to track the skin tumor burden in MF/SS. It measures the percentage total body-surface area (TBSA, %) involvement separately for patches, plaques, and tumors within 12 body regions using the patient's palm and fingers representing 1% of TBSA. Patients with erythroderma are assessed for percentage of TBSA involved with patches and/or plaques. The percentage of TBSA for each lesion type is multiplied by a number (patch = 1, plaque = 2; tumor = 4) and summed to derive the mSWAT score. The mSWAT for each patient will be determined by the same individual at all study visits.

A complete response (CR) requires 100% clearing of skin disease and a partial response (PR) requires $\geq 50\%$ reduction in the mSWAT score compared with baseline. CR/PR requires confirmation by repeat assessment after ≥ 4 weeks. Stable disease is defined as less than 50% reduction to less than 25% increase in the mSWAT score compared with baseline. PD is defined as $\geq 25\%$ increase in the mSWAT score from baseline or $\geq 50\%$ increase in the sum of the products of the greatest diameters of pathologically positive lymph nodes compared with baseline.

Time to response is the time from the first treatment dose until the patient first meets the criteria for a 50% decrease in the GR score. The duration of response (DOR) is the time from first CR/PR until the GR score is increased from nadir to more than 50% of the difference between the baseline and nadir scores. Time to progression (TTP) is the time from start of treatment until PD. If patients go off treatment for any purpose, this date is used for determination of TTP and/or DOR.

Table 9: Calculating mSWAT Score

Body Region	% BSA in Body Region	Assessment of Involvement in Patient's Skin		
		Patch¹	Plaque²	Tumor³
Head	7			
Neck	2			
Anterior trunk	13			
Arms	8			
Forearms	6			
Hands	5			
Posterior trunk	13			
Buttocks	5			
Thighs	19			
Legs	14			
Feet	7			
Groin	1			
Subtotal of lesion BSA				
Weighing factor		x1	x2	x4
Subtotal lesion BSA x weighing factor				

NOTE: mSWAT score equals summation of each column line.

Abbreviations: BSA, body surface area; mSWAT, modified Severity Weighted Assessment Tool.

¹ Any size lesion without induration or significant elevation above the surrounding uninvolved skin; poikiloderma may be present

² Any size lesion that is elevated or indurated; crusting, ulceration, or poikiloderma may be present.

³ Any solid or nodular lesion \geq 1cm in diameter with evidence of deep infiltration in the skin and/or vertical growth.

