16 APPENDIX

16.1 APPENDIX A: PERFORMANCE STATUS CRITERIA

ECOG Performance Status Scale		Karnofsky Performance Scale	
Grade	Descriptions	Percent	Description
0	Normal activity. Fully active, able to carry on all pre-disease performance without restriction.	100	Normal, no complaints, no evidence of disease.
		90	Able to carry on normal activity; minor signs or symptoms of disease.
1	Symptoms, but ambulatory. Restricted in physically strenuous activity, but ambulatory and able to carry out work of a light or sedentary nature (e.g., light housework, office work).	80	Normal activity with effort; some signs or symptoms of disease.
		70	Cares for self, unable to carry on normal activity or to do active work.
2	In bed <50% of the time. Ambulatory and capable of all self-care, but unable to carry out any work activities. Up and about more than 50% of waking hours.	60	Requires occasional assistance, but is able to care for most of his/her needs.
		50	Requires considerable assistance and frequent medical care.
3	In bed >50% of the time. Capable of only limited self-care, confined to bed or chair more than 50% of waking hours.	40	Disabled, requires special care and assistance.
		30	Severely disabled, hospitalization indicated. Death not imminent.
4	100% bedridden. Completely disabled. Cannot carry on any self-care. Totally confined to bed or chair.	20	Very sick, hospitalization indicated. Death not imminent.
		10	Moribund, fatal processes progressing rapidly.
5	Dead.	0	Dead.

16.2 APPENDIX B: GLOBAL RESPONSE SCORE AND DEFINITIONS OF RESPONSE IN SKIN, LYMPH NODES, VISCERA, AND BLOOD

Global Response Score					
Global Score	Definition	Skin	Nodes	Blood	Viscera
CR	Complete disappearance of all clinical evidence of disease	CR	All categories have CR/NI		
PR	Regression of measurable disease	CR	All categories do not have a CR/NI and no category has a PD		
		PR	No category has a PD and if any category involved at baseline at least one has a CR or PR		
SD	Failure to attain CR, PR, or PD representative of all disease	PR	No category has a PD and if any category involved at baseline, no CR or PR in any		
		SD	CR/NI, PR, SD in any category and no category has a PD		
PD	Progressive disease	PD in any category			
Relapse	Recurrence of disease in prior CR	Relapse in any category			

Abbreviations: CR, complete response; NI, noninvolved; PR, partial response; PD, progressive disease; SD, stable disease.

Response in Skin	
Response	Definition

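### Section 6.3.1.2 adopts the Appendix B global score for CTCL, then adds unlabelled mSWAT-based response categories that conflict with it in patients with disease outside the skin

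*Combined protocol and SAP*

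**What the plan says.** Section 6.3.1.2 opens by saying that the Global Response (GR) score of Appendix B "will be used for assessing response in patients with CTCL". It adds that the "GR score incorporates separate responses in each component of the TNBM staging", and sets a floor: "No patient with a global OR should have less than a PR in the skin". It next introduces mSWAT, which "is an instrument utilized to track the skin tumor burden in MF/SS".

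The following paragraph gives response categories without saying which level they belong to: "A complete response (CR) requires 100% clearing of skin disease and a partial response (PR) requires" a fall of at least 50% in mSWAT from baseline. SD is then defined purely as an mSWAT range, from a fall of under 50% to a rise of under 25%. PD is a rise of at least 25% in mSWAT, or a rise of at least 50% in a nodal measure, the "increase in the sum of the products of the greatest diameters of pathologically positive lymph nodes compared with baseline".

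Appendix B (section 16.2) combines four compartments:
- Global CR needs skin CR and every other category in CR or not involved.
- Skin CR is only a global PR when "All categories do not have a CR/NI and no category has a PD".
- Skin PR is a global PR when nothing progresses and, if any other category was involved, at least one of them is in CR or PR.
- Skin PR is a global SD when "No category has a PD and if any category involved at baseline, no CR or PR in any".

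Appendix B also withholds skin PR when new tumors appear in patients whose skin disease was T1, T2 or T4 only.

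**The concern.** The second set of categories reads as an overall classification, although the section has just named a different one. The terms CR, PR, SD and PD carry no qualifier. PD contains a nodal criterion, so the paragraph is not a pure skin scale. It cannot be a full global scale either, since it has no blood or visceral criterion and no new-tumor condition. Section 6.3.1 names both the Global Response Score and mSWAT for CTCL without saying which decides.

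At stake is who counts as a responder in ORR and CR rate, both secondary endpoints. Section 10.4.3 wants every report of response rates to cover all patients, so CTCL patients from the escalation cohort enter these rates. Section 1.10.3 indicates that there were some. If the mSWAT paragraph is applied as the overall rule, patients whose nodes or blood have not responded can be counted as responders.

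**Working it through.** The plan gives no figure to reproduce. The check sets the two rules side by side and then sizes one reclassification.

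**Step 1: the same patient under both rules.**

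| Patient | Categories in 6.3.1.2 | Appendix B | Rate that moves |
|---|---|---|---|
| Skin cleared; involved nodes unchanged | can be read as CR | PR | CR rate only |
| mSWAT down 60%; involved nodes unchanged | PR | SD | ORR |
| mSWAT down 60%; new tumors where baseline was T1, T2 or T4 only | PR | PD | ORR |
| Skin cleared; progression in viscera | can be read as CR | PD | both |
| Skin-only disease; skin cleared or mSWAT down 60%; no new tumors | CR or PR | same | none |

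The second row is the firmest. A 60% fall is outside the SD range (under 50%). It is short of CR (100%). With nodes unchanged it is not PD. Only PR is left in 6.3.1.2, while Appendix B gives SD.

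The first row is weaker. A cleared skin also passes the 50% threshold, so a reader who treats full clearance as necessary but not sufficient for CR could still arrive at PR.

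**Step 2: how much of the Appendix B table is involved.** Let nodes, blood and viscera each be not involved, CR, PR or SD, with no progression. That gives 4³ = 64 combinations.
- Skin CR: global CR needs all three in CR or not involved, 2³ = 8 cells. The other 64 − 8 = 56 are PR.
- Skin PR: global SD needs all three in SD or not involved, with at least one involved, 2³ − 1 = 7 cells. The other 64 − 7 = 57 are PR.
- Skin SD: all 64 are SD.

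These are table cells, not patients. They show that the shift affecting ORR is confined to one pattern: skin PR with every other involved compartment unresponsive.

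**Step 3: size per patient.** Section 3.4.1 puts 20 patients on study when escalation was fully accrued. Section 10.2 gives 27 as the planned maximum of evaluable patients.
- 1/20 = 5.0 percentage points
- 1/27 = 3.7 percentage points

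**Step 4: does the rest of 6.3.1.2 settle the reading?** No. Duration of response starts at the first CR or PR, again unqualified. Time to response is tied to a 50% fall in the GR score. The Appendix B global score is a category and cannot fall by 50%; of the two CTCL scores, only mSWAT is numeric. The section therefore mixes the two scores itself.

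**The case against.** The strongest reply is that the governing rule is already in place. The section's first sentence adopts Appendix B with all four compartments. The disputed sentence directly follows the introduction of a skin instrument, and it says what CR and PR *require*, which is a necessary condition. Its 100% and 50% thresholds are those of the skin table in Appendix B. Read as the skin component, the CR and PR thresholds do not conflict with Appendix B.

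Much of this stands. A reader might infer that 6.3.1.2 defines CTCL response by skin clearance alone; the section's opening does not support that. A reader might also infer that Appendix B needs all other involved compartments to respond. It does not: skin CR with stable disease elsewhere is a global PR, and skin PR needs only one involved category to respond.

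What does not stand is that the skin-component reading resolves the whole paragraph. It cannot explain a nodal criterion for PD, and SD is stated as a definition rather than a requirement.

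The scope is also narrow. ORR and CR rate are secondary in a phase 1 study whose primary endpoints are MTD and adverse events, and CTCL is now excluded (2.1.1.1 and 2.1.2.4). That limits the weight of the point but does not classify the patients already treated.

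**Conclusion.** The concern holds as an internal conflict between two sets of categories. In patients with disease outside the skin, 6.3.1.2 can give CR where Appendix B gives PR (CR rate only) and PR where Appendix B gives SD (ORR). The omitted new-tumor condition and the missing blood and visceral criteria add further mismatches; the new-tumor one can arise even in skin-only disease. Otherwise the two sets agree on CR and PR in skin-only disease.

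The size is 5.0 points per reclassified patient on 20, or 3.7 on 27. Neither denominator is a final analysis count. A reader might infer a total bias by guessing how many patients had CTCL and how many had a discordant response, or infer that reported activity is already inflated. The documents support neither: they give no CTCL count and no discordance rate, and do not show that the mSWAT paragraph was ever applied as the overall rule.

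**What to change.** In section 6.3.1.2:
- Label the mSWAT thresholds as response in the skin compartment, with the new-tumor condition from Appendix B.
- Move the nodal PD criterion to the nodal component.
- State that overall CR, PR, SD and PD for CTCL, and so ORR and CR rate, come only from the Appendix B global table.
- Report skin response separately.
- Name the score that time to response and duration of response refer to.

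The cost is a few sentences and a re-read of the CTCL patients already treated. There are two downsides. The reported CTCL response rate may be lower. Some patients may also lack a full compartment assessment, because note 19 to the study calendar lets skin scoring replace imaging in predominantly cutaneous disease. The plan should say in advance how such patients are classified and keep them in the all-patient denominator.
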